1 STATISTICAL ANALYSIS CONSIDERATIONS

1.1 Sample Size

As a feasibility RCT, no formal power calculation will be undertaken (Eldridge et al. 2016). One of the aims of the study is to select the most appropriate primary and secondary outcome measures and inform the sample size for calculation of the future RCT. There is no consensus on the feasibility study recommended number of participants, suggested numbers ranging from 20 -70 (Whitehead et al., 2016). Therefore, this feasibility study aims to recruit 60 participants.

1.2 Statistical Analysis

Participants will be recruited for a minimum of three days and a maximum of eight days. The planned recruitment period is three-six months. Participants initial evaluation will be on the 3rd day of ICU admission and the second one will be on the 6th day. The follow-up rate is estimated to be 50% or more. An extended CONSORT flow diagram will be used to present descriptive data on screening, enrolment, intervention allocation, and follow-up. It will also show any deviations from protocol, for example, participants developed any unexpected side effects. The modified CPIS will be calculated for each study participant within each study group to compare VAP incidence in each group which will be represented through cross tables and figures. Other descriptive data findings will be also represented through tables/figures.

Data will be presented as frequency and percentages (qualitative variables) and mean \pm SD (quantitative continuous variables). Chi-square (x2) will be used for comparison of categorical variables and will be replaced by Fisher exact test (FET) or Mont Carlo Exact test if the expected value of any cell is less than 5. The student's t-test will be used for the comparison of continuous quantitative variables. For continuous quantitative variables that will not normally distributed, Median will be used as a central tendency measure. The Mann Whitney test (Z) will be used to compare the three groups. The difference will be considered significant at P \leq 0.05. Statistical advised will be sought.

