1.3 Analysis populations

All analyses and data summaries will be conducted on the intention-to-treat (ITT) population which is defined as all enrolled participants and followed up at least for 3 days in ICU, and also critical care

Single-used versus MultiPIE-used endotracheal suCtIon cAtheters in mechanically ventiLated ICU patients: the SPECIAL-ICU trial. Statistical Analysis Plan Version 1 dated 14th of December 2023.

nurses who conducted the study. Withdrawn Patients and critical care nurses who will refuse to be interviewed will not be included in the analysis.

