1.6 Primary analysis

The aim of this primary analysis is to assess the feasibility of delivering the intervention in the study settings, and selection of primary and secondary outcome measures. Components to be analysed are:

feasibility of a trial by producing:

- CONSORT diagram
- Timing of follow-up assessments
- Time it took to recruit participants
- Number of critical care nurses willing to participate
- Randomization technique effectiveness

feasibility of the intervention by producing:

- Critical care nurses' acceptability of the intervention
- Method of delivering the intervention to each study arm

Selection of primary/secondary outcomes

comparing outcomes of each study group

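### SAP 1.2 classes unexpected side effects as protocol deviations, and the 1.3 exclusion would drop patients withdrawn because of one from any by-arm side-effect summary

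*SAP*

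**What the plan says.** Section 1.2 of the SAP describes the flow diagram: "An extended CONSORT flow diagram will be used to present descriptive data on screening, enrolment, intervention allocation, and follow-up". The next sentence adds: "It will also show any deviations from protocol, for example, participants developed any unexpected side effects". The SAP mentions side effects nowhere else and gives no other example of a deviation.

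On clinical outcomes, the same section uses the modified CPIS to "compare VAP incidence in each group which will be represented through cross tables and figures". It then says: "Other descriptive data findings will be also represented through tables/figures".

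Section 1.3 applies one population to every analysis and data summary. That population is called intention-to-treat and is "defined as all enrolled participants and followed up at least for 3 days in ICU". The section ends: "Withdrawn Patients and critical care nurses who will refuse to be interviewed will not be included in the analysis".

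Section 1.5 puts the emphasis on description and confidence intervals rather than testing. Section 1.6 lists the CONSORT diagram first among the products that show whether a trial is feasible. Under feasibility of the intervention it lists "Method of delivering the intervention to each study arm". Its list of components has no side-effect or safety item.

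**The concern.** A protocol deviation is a departure from planned conduct, such as a patient receiving the other catheter policy or an evaluation not being done. A side effect in a patient who was treated as allocated is something that happened to the patient while the plan was being followed. Section 1.2 puts the second under the label of the first.

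Two things are at stake.

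- **Feasibility.** The diagram is a primary product. If side effects are entered as deviations, an arm in which the catheter policy was delivered exactly as planned, but some patients had side effects, can look like an arm in which the policy could not be delivered. These findings call for different decisions about the future trial: one concerns training or logistics, the other tolerability.
- **Side-effect rates.** A by-arm summary made under the plan as written would use the 1.3 population. A patient withdrawn because of a side effect is then absent from both numerator and denominator. Such patients are the ones a side-effect summary most needs to count.

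**Working it through.** The SAP states no side-effect rate, deviation count or withdrawal rate, so it has no figure to reproduce. The check is mainly a reading of sections 1.2, 1.3, 1.5 and 1.6 together.

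**Step 1: classification.** Section 1.2 says the diagram shows deviations and gives side effects as the instance. The misclassification is therefore stated. It is not a gap that an unseen protocol would fill, because a protocol definition of side effects would leave this sentence as it is.

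**Step 2: where the label matters.** Section 1.6 makes the diagram a primary feasibility product. It sets no limit on the number of deviations and lists no deviation rate. The mixing therefore affects how the diagram is read, and no stated decision rule turns on it.

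**Step 3: what a side-effect table would contain.** The general line in 1.2 on other descriptive findings could cover such a table. Section 1.3 would then apply to it, so withdrawn patients, and those followed for under three days, would be left out. The SAP does not say that a side effect leads to withdrawal, so this loss is conditional on its doing so.

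**Step 4: illustration of the 1.3 exclusion.** All counts here are assumptions. Section 1.1 gives 60 participants in total. Two equal arms would give 60/2 = 30 per arm, but the SAP states no allocation ratio, and one sentence in 1.2 speaks of three groups, which would give 60/3 = 20. Suppose 3 patients in an arm have a side effect and *w* of them are withdrawn because of it. Among all allocated patients the proportion is 3/*n*. In the 1.3 population it is (3 − *w*)/(*n* − *w*).

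With *n* = 30:

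| *w* | 1.3 population | Percentage |
|---|---|---|
| 0 | 3/30 | 10.0% |
| 1 | 2/29 | 6.9% |
| 2 | 1/28 | 3.6% |
| 3 | 0/27 | 0% |

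Exact (Clopper-Pearson) 95% intervals for the two extremes:

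| *n* | All allocated | 1.3 population, *w* = 3 |
|---|---|---|
| 30 | 3/30: 2.1% to 26.5% | 0/27: 0% to 12.8% |
| 20 | 3/20: 3.2% to 37.9% | 0/17: 0% to 19.5% |

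With no events, the upper limit is 1 − 0.025^(1/*m*), where *m* is the number analysed: 1 − 0.025^(1/27) = 12.8% and 1 − 0.025^(1/17) = 19.5%.

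The direction is the same for both arm sizes. The whole shift comes from the exclusion in 1.3 and the assumed withdrawals. None of it comes from the deviation label in 1.2.

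**The case against.** The strongest reply is that this is loose wording in one sentence. The sentence may mean side effects that led to a departure from the allocated procedure. The diagram would still display the events. If it splits by arm after allocation, as such diagrams normally do, a reader could work out a count over those allocated. Section 1.6 has no deviation threshold, so no planned decision is shown to change. Safety definitions and reporting are commonly left to the protocol.

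Much of this stands, and it rules out three stronger readings that a reader might infer.

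- *The plan hides harm from a catheter policy.* It does not: VAP, a harm plausibly linked to that policy, is compared by group in 1.2.
- *Side effects will be reported only in the diagram.* The SAP names them only there. It does not exclude reporting elsewhere, and its line on other descriptive findings leaves room for it.
- *Both the events and the denominator are lost.* The diagram would show the events alongside the numbers allocated, although under the wrong label.

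What the reply does not remove is narrower. The sentence as written still classes an outcome as a deviation, and if something else was meant, it needs to say so. A mixed deviation box gives neither a side-effect proportion nor an interval, although 1.5 favours interval estimation. Any table that did give them would fall under 1.3, which is an explicit rule and would leave out withdrawn patients.

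**Conclusion.** The point holds in two parts. First, 1.2 misclassifies unexpected side effects as protocol deviations, and so mixes outcomes with departures from conduct in a primary feasibility product. Second, 1.3 would leave patients withdrawn because of a side effect out of any by-arm side-effect summary.

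The size of neither effect can be estimated from the SAP. The second part matters only if some patients are withdrawn because of a side effect, which the SAP neither states nor rules out. The change from 10% to 0% is the extreme of an assumed case and shows only how the exclusion works. The lack of a safety section is not part of the point, since the protocol may cover it. This is a modest correction that should be made before the data are summarised.

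**What to change.** In 1.2, replace the side-effect example with a true departure, such as a patient receiving the other catheter policy or a missed evaluation.

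Also in 1.2, state that side effects are summarised by arm as the number and percentage of patients with at least one event, with an exact 95% CI. The denominator is all allocated patients, with withdrawn patients counted up to the time of withdrawal. Add a matching line to 1.3 saying that this summary is an exception to its exclusion.

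The cost is one changed sentence, one added statement with its cross-reference, and one descriptive table. The diagram already requires side effects to be recorded, so no new procedure or visit is needed.

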1.5 Outcome analysis

As a feasibility study, analysis will focus on descriptive statistics and confidence interval (CI) estimation rather than formal hypothesis testing.

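### Does the SAP need to say which CPIS evaluation defines VAP, and how to count a patient without a day-6 score?

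*SAP*

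**What the plan says.** Section 1.2 gives the schedule: "Participants initial evaluation will be on the 3rd day of ICU admission and the second one will be on the 6th day". The same section describes the VAP analysis: "The modified CPIS will be calculated for each study participant within each study group to compare VAP incidence in each group". It promises tables and figures in the plural and does not say that there will be a single VAP table. It expects follow-up of at least 50% without tying that figure to a day, and lets participation last from three to eight days.

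Section 1.3 sets the denominator for every analysis and calls it the ITT population. Membership is worded as follows: "defined as all enrolled participants and followed up at least for 3 days in ICU". It also removes withdrawn patients from the analysis.

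Section 1.1 states that "this feasibility study aims to recruit 60 participants", with no power calculation. Section 1.5 says that "analysis will focus on descriptive statistics and confidence interval (CI) estimation rather than formal hypothesis testing". Section 1.6 makes feasibility the primary analysis, lists "Timing of follow-up assessments" among its components, and includes the selection of outcome measures.

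**The concern.** With two evaluations, VAP incidence has several readings: VAP on day 3, VAP on day 6 among those scored, VAP at either evaluation, or new VAP after day 3. The SAP chooses none of them. A patient who dies, is extubated or leaves the ICU between the evaluations, without having withdrawn, could be in the analysis set with a day-3 score only. The SAP does not say whether that patient counts as a non-case, drops out of the denominator or is shown separately.

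Two analysts could therefore produce different VAP tables from the same data. Because the study is meant to inform the sample size of a later trial, the event rate carried forward could depend on an unrecorded choice.

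**Working it through.** The SAP gives no VAP rate, no day-6 retention and no derived sample size, so there is no stated figure to reproduce. The check is of how far the reading matters, and whether any reading that the text allows is unsound.

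**Arm size.** The total of 60 is from section 1.1. Equal allocation is assumed. The document's title suggests two arms, while section 1.2 mentions three groups ("The Mann Whitney test (Z) will be used to compare the three groups").
- Two arms: 60/2 = 30, so one case is 1/30 = 3.3 percentage points.
- Three arms: 60/3 = 20, so one case is 1/20 = 5.0 points.

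These are minimum shifts, since the analysed arm can be smaller than the recruited arm.

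**Patients without a day-6 score.** For assumed retention f to day 6, the number unscored in an arm of N is N × (1 − f).

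| f | N = 20 | N = 30 |
|---|---|---|
| 50% | 10 | 15 |
| 70% | 6 | 9 |
| 90% | 2 | 3 |
| 100% | 0 | 0 |

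**Day 3 against cumulative by day 6.** The counts are assumed; intervals are Wilson 95%.
- Arm of 20, 3 cases on day 3 and 3 new on day 6: 3/20 = 15.0% (5.2 to 36.0), or 6/20 = 30.0% (14.5 to 51.9).
- Arm of 30, 5 cases and 4 new: 5/30 = 16.7% (7.3 to 33.6), or 9/30 = 30.0% (16.7 to 47.9).

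The shifts are 15.0 and 13.3 points. The day-3 intervals are 36.0 − 5.2 = 30.8 and 33.6 − 7.3 = 26.3 points wide, so each shift is about half the width of the interval printed beside it.

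**Effect of the counting rule.** Assume 10% VAP on day 3, 20% new VAP by day 6 among the rest, half of patients scored on day 6 at random, and day-3 cases persisting.
- Day 3: 10%.
- New after day 3, among those scored: 20%.
- Day 6 among those scored: 0.10 + 0.90 × 0.20 = 28%.
- Either evaluation, unscored counted as non-cases: 0.10 + 0.90 × 0.20 × 0.5 = 19%.
- Either evaluation, unscored counted as cases: 0.10 + 0.90 × (0.20 × 0.5 + 0.5) = 64%.

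The last figure is an extreme bound, not something an analyst would report as incidence. The other four are ordinary descriptive quantities with different meanings. Cases over all analysed patients, in particular, is a legitimate cumulative incidence when patients die or are extubated.

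**Whether the gap exists at all.** Section 1.3 does not say when its three days begin. If they run from ICU admission, a patient may leave before day 6 and stay in the set. If they run from the initial evaluation, day 3 + 3 = day 6, so every patient in the set reaches the second evaluation and the question largely disappears. On either reading, withdrawn patients are already dealt with by exclusion. What may be left is the group who die, are extubated or are discharged between the two evaluations.

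**The case for a change.** The best case for a change is that the missing-score half does not depend on the protocol. The SAP itself defines the analysis set and applies it to every analysis, so it should say how a patient with no second score is counted. Descriptive work still needs a numerator and a denominator. Sections 1.1 and 1.6 tie the outcome results to the design of the next trial, and the CONSORT diagram, though it shows losses, does not say which score the VAP table uses. Two sentences written before analysis would remove a choice made after seeing the data.

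It stands that nothing in the SAP supplies the rule, and that the reading can move an arm's figure by several cases. It does not stand that the plan leads to a wrong result. A table of VAP at each evaluation, with the number scored beside it, is compatible with section 1.2 and lets a later planner take whichever rate is needed.

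Nor is the obvious repair free of difficulty. Keeping every day-3 case who leaves early would clash with section 1.3 for those who withdrew. A cumulative figure over the whole set makes a day-3-negative, unscored patient a non-case without saying so. If day 3, which section 1.2 calls the initial evaluation, serves as a baseline, that figure would count existing VAP as new. Choosing among these without the protocol could contradict the outcome definition there.

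**Conclusion.** No change is needed. The SAP is silent on the point; it does not state a wrong rule. The time point is outcome-definition content that the unseen protocol may well hold. The count of unscored patients is a detail that competent analysts fill by showing scored and unscored numbers at each evaluation. Some openness also fits a study that treats assessment timing and outcome selection as questions to be answered.

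The possible size is 3.3 or 5.0 percentage points per additional case, assuming equal arms of 30 or 20. The larger contrasts above rest on assumed VAP rates and, for the counting-rule figures, on assumed 50% retention to day 6, which the SAP does not state. No direction of bias and no effect on a confirmatory conclusion can be shown, because feasibility is the primary analysis and the emphasis is on description and interval estimation. The conclusion assumes that the VAP results are reported with their denominators.

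### Two evaluations per patient are planned with losses expected between them, but no analysis method in the SAP links them; one repeated-measures model would be a cheap improvement

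*SAP*

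**What the plan says.** Section 1.2 sets the schedule: "Participants initial evaluation will be on the 3rd day of ICU admission and the second one will be on the 6th day". It also says "Participants will be recruited for a minimum of three days and a maximum of eight days", which reads as time in the study and lets a patient leave before the second evaluation, and "The follow-up rate is estimated to be 50% or more".

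The same section lists the comparison methods. For categorical data, "Chi-square (x2) will be used for comparison of categorical variables", with an exact test when expected counts are small. For continuous data, "The student's t-test will be used for the comparison of continuous quantitative variables", with Mann-Whitney when the data are not normal. The one clinical outcome it names is VAP incidence, derived from the modified CPIS and shown in cross tables.

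Section 1.3 applies all analyses to patients followed for at least three days in ICU and leaves out withdrawn patients. Section 1.5 puts description and confidence intervals ahead of testing. Section 1.1 plans 60 participants without a power calculation and gives as aims the choice of outcomes and to "inform the sample size for calculation of the future RCT". Section 1.6 bases the choice of outcomes on comparing the study groups.

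**The concern.** The design yields two measurements on the same patient, and the second will be missing for some. None of the named methods uses that pairing. Chi-square, Fisher and Mann-Whitney compare independent groups. The t-test has Mann-Whitney as its non-normal counterpart, which points to the unpaired form. No change analysis, day-3 adjustment or repeated-measures model appears anywhere in the SAP.

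If day 6 is compared on its own, a patient who left on day 4 or 5 belongs to the section 1.3 population but contributes nothing, although a day-3 value exists. Three things follow:

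- The day-6 estimate is less precise than the data allow.
- A difference between the day-3 and day-6 group means mixes real change with a change in who is still there.
- If departure is tied to condition differently in the arms, the day-6 comparison between arms is biased.

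The means, SDs and intervals are what the trial will use to choose outcomes and size the next trial, so they matter even in a descriptive study.

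**Working it through.** The SAP derives no SD, effect size or power, so there is no figure of its own to reproduce beyond the planned 60.

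**Numbers at day 6.** Inputs: 60 participants (section 1.1) and 50% follow-up (section 1.2). Applying the 50% to day 6 is an assumption. 60 × 0.50 = 30. The trial title names two ways of using catheters, but the Mann-Whitney sentence in section 1.2 refers to three groups, so both splits are shown. The approximate 95% CI half-width for a difference between two arms, in SD units, is 1.96 × √(2/n).

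| Arms | n per arm, day 3 | Half-width | n per arm, day 6 | Half-width |
|---|---|---|---|---|
| 2 | 30 | 0.51 | 15 | 0.72 |
| 3 | 20 | 0.62 | 10 | 0.88 |

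**Precision under random loss.** Let ρ be the day-3/day-6 correlation (assumed 0.5 to 0.7). The variance with linking, relative to the variance without, for two arms is

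[(1 − ρ²)/15 + ρ²/30] × 15 = 1 − ρ²/2.

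For ρ = 0.5, 0.6, 0.7 this gives 0.875, 0.82, 0.755. Simulation (20,000 trials per setting) gave 0.89, 0.84, 0.76, a saving of about 11% to 24%. In patients: 15/0.89 = 16.9 and 15/0.76 = 19.7, so about 2 to 5 extra on top of 15 per arm. With 10 and 20 in place of 15 and 30 the ratio is the same, and the gain is about 1 to 3 per arm (10/0.89 = 11.2; 10/0.76 = 13.2).

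**Shift from who remains, with no true change or effect.** Assume a score with SD 2, and that patients below the day-3 mean leave with probability 0.75 and the others with 0.25. Half leave. The mean of a half-normal is 0.798 SD, so the day-3 mean of those who stay is raised by (0.75 − 0.25) × 0.798 × 2 = 0.80 points. Their day-6 mean is raised by ρ × 0.80 = 0.40, 0.48, 0.56 points for ρ = 0.5, 0.6, 0.7.

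- Same pattern in both arms: the between-arm difference stays at about 0, but each arm's day-6 mean lies 0.40 to 0.56 points above its day-3 mean.
- Pattern in one arm only: the between-arm difference on day 6 is wrong by 0.40 to 0.56 points.
- Linked model: error about 0 in both cases. This follows from the set-up, because departure was made to depend on the day-3 value alone.

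**Second departure model.** Let the probability of staying be logistic(b × day-3 score), in SD units. With b = 1 in one arm and 0 in the other, the day-6 difference among those present is 0.21, 0.29, 0.37 SD for ρ = 0.5, 0.7, 0.9, and about 0 after conditioning on day 3. With b = 1 in both arms it is about 0 without any adjustment.

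**A paired test would not repair this.** In the same model with b = 1 and ρ = 0.5, the day-6 mean of those present lies 0.21 SD above the day-3 mean of everyone. The mean paired change among those same patients is −0.21 SD. Both are artefacts, since nothing truly changed. The model has to keep the day-3 values of those who left.

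**The case against.** A reader might infer that the SAP commits itself to a separate day-6 test on half the patients and that this test will be biased. The text does not support that. It never says which evaluation is tested, does not label the t-test unpaired, and does not attach the follow-up figure to day 6; 50% is also a floor. Endpoint timing may be set out in the protocol.

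The bias figures come from a chosen departure pattern. If both arms lose patients in the same way, there is no between-arm bias. Even in the one-arm scenario, 0.40 to 0.56 points is 28% to 39% of the CI half-width at 15 per arm, 1.96 × 2 × √(2/15) = 1.43 points. That the model removes the error is built into the assumption about departure, and nothing in the SAP supports that assumption for ICU patients.

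The figures also concern a continuous score, whereas the clinical outcome that section 1.2 names is VAP incidence. A repeated-measures model for a score does not serve that outcome, and cross tables and an extended CONSORT diagram are already planned. The within-patient correlation can be calculated from the data whichever test is named, and would be imprecise: with 30 pairs and r = 0.6, its 95% CI is about 0.31 to 0.79. Section 1.5 makes the analysis descriptive.

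All of this stands, and it limits the point to an improvement in method. It does not remove the gap: the SAP does name its comparison methods, and none of them uses the two evaluations together.

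**Conclusion.** The point holds as a cheap improvement, not as a demonstrated error in a planned result. Two evaluations are scheduled, loss is expected, and on the natural reading every named comparison treats groups as independent, with nothing linking a patient's two values.

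The firmest consequence is a modest loss of precision if day 6 is compared alone: about 11% to 24% of variance, given half the patients seen at day 6, random loss and a correlation of 0.5 to 0.7. Next is the risk of reading a change in who remained as a change in condition; this arises within an arm even when departure follows the same pattern in every arm. Bias between arms is only conditional: it needs departure to depend on condition differently by arm, and the SAP gives no ground for expecting that. None of the score-based figures carries over to VAP incidence.

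**What to change.** For any score or continuous outcome measured on both days, such as the modified CPIS score, replace separate t or Mann-Whitney comparisons with one repeated-measures model. Use group, day and group-by-day, an unstructured covariance for the two days, and both days as outcomes. Include every participant with at least one evaluation, which also brings the analysis closer to the section 1.3 population. Report the between-group difference on each day with its 95% CI, the SD on each day and the within-patient correlation. The model works with two or three groups.

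For VAP status, cross-tabulate day-3 against day-6 status by arm, with a further column for no day-6 evaluation and its reason. State in section 1.2 whether the follow-up figure refers to day 6.

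The cost is SAP wording and a little more analysis; no new data are needed. The downside is that the model assumes departure is explained by the day-3 value. Deaths and other early departures must therefore be shown separately by arm, and the estimates treated as descriptive, in line with section 1.5.

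### Section 1.2 declares group differences significant at P ≤ 0.05, section 1.5 sets the analysis towards confidence intervals rather than testing, and nothing says which governs

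*SAP*

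**What the plan says.** Section 1.2 (Statistical Analysis) prescribes chi-square for categorical variables, replaced by Fisher's exact or a Monte Carlo exact test when expected counts are small, Student's t-test for continuous variables, and Mann-Whitney for non-normal ones. It then sets the decision rule: "The difference will be considered significant at P" ≤ 0.05. The summaries it lists are frequencies, percentages, mean with SD, and median. It lists no confidence interval. It also says that VAP incidence, derived from the modified CPIS, will be compared between groups in cross tables, so the categorical test and its threshold apply to VAP.

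Section 1.5 (Outcome analysis) says that "analysis will focus on descriptive statistics and confidence interval (CI) estimation rather than formal hypothesis testing". This is the only mention of confidence intervals in the SAP, and it gives no level, method or effect measure.

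Two other sections bear on the point. Section 1.1 states: "As a feasibility RCT, no formal power calculation will be undertaken". Section 1.6 (Primary analysis) lists "comparing outcomes of each study group" under the selection of primary and secondary outcomes, without saying whether P values or intervals inform that selection.

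**The concern.** The section that lists the methods specifies only tests and a threshold. The section that states the inferential approach asks for estimation instead. Declaring a difference significant at a fixed threshold is formal hypothesis testing, so an analyst has to choose which section to follow, and two analysts could produce different reports from the same plan.

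The choice affects what the trial appears to conclude. If section 1.2 is followed, each outcome comparison, VAP included, receives a verdict that the trial was not sized to give. A non-significant VAP result could be taken as evidence that single-use and multiple-use catheters are equivalent. The group comparison is also an input to choosing outcomes for the future trial, and P values from a trial of this size are a poor basis for that choice. If section 1.5 is followed, intervals are promised, but with no effect measure named it is unclear what the VAP interval would be an interval for.

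**Working it through.** **Side-by-side reading.** The conflict itself needs no arithmetic.

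| Question | Section 1.2 | Section 1.5 |
|---|---|---|
| Tests with a threshold? | Yes, P ≤ 0.05, unqualified | Not the focus |
| Confidence intervals? | None named | Yes, but no level or effect measure |
| Status of P values? | Not stated | Not stated |
| Which section prevails? | Not stated | Not stated |

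**What the threshold could deliver.** The SAP has no power figure to reproduce: 60 was chosen from a quoted range of 20 to 70. The rest is illustration.

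Inputs from the SAP:
- 60 participants to be recruited (section 1.1).
- "The follow-up rate is estimated to be 50% or more" (section 1.2), so 30 to 60 evaluable if that rate equals the evaluable fraction: 60 × 0.50 = 30.
- Number of groups: the trial title names two strategies, while section 1.2 says "The Mann Whitney test (Z) will be used to compare the three groups". Both cases are shown.

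Assumptions: equal allocation, two-sided tests, and VAP rates that double between arms, since the SAP gives no rates.

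Evaluable patients per arm:
- two groups: 60/2 = 30 down to 30/2 = 15
- three groups: 60/3 = 20 down to 30/3 = 10 (figures below are then for one pairwise comparison)

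Power was computed by exact enumeration over both binomial distributions under the SAP's rule: uncorrected chi-square if all expected counts are at least 5, otherwise Fisher's exact test, rejecting at P ≤ 0.05.

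| Assumed VAP rates | 30 per arm | 20 | 15 | 10 |
|---|---|---|---|---|
| 10% v 20% | 13.3% | 8.0% | 4.2% | 1.2% |
| 15% v 30% | 27.2% | 17.3% | 9.1% | 3.4% |
| 20% v 40% | 39.2% | 28.4% | 16.0% | 5.8% |
| 30% v 60% | 66.3% | 46.3% | 35.7% | 12.3% |
| 40% v 80% | 90.5% | 75.3% | 59.1% | 25.3% |

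95% interval half-width for the risk difference = 1.96 × √[(p₁(1−p₁) + p₂(1−p₂))/n].

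For 20% v 40% at 30 per arm: 1.96 × √[(0.16 + 0.24)/30] = 1.96 × 0.1155 = 0.226, or 22.6 points.

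| Assumed VAP rates | 30 per arm | 20 | 15 | 10 |
|---|---|---|---|---|
| 15% v 30% | 20.8 points | 25.5 | 29.4 | 36.0 |
| 20% v 40% | 22.6 points | 27.7 | 32.0 | 39.2 |

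**One possible result.** Suppose VAP occurs in 9/30 and 5/30.
- Expected counts are 7 and 23 in each arm, so chi-square applies: 60 × (9×25 − 5×21)² / (30×30×14×46) = 864,000/579,600 = 1.49, P = 0.22.
- The observed difference is 30.0% − 16.7% = 13.3 points. Its Newcombe 95% interval runs from −8 to +33 points.

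Section 1.2 labels this result not significant. The interval shows that it is compatible with anything from a modest difference in one direction to a very large one in the other.

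**The case against.** The strongest reply is that the conflict is soft. To focus on estimation sets a priority and does not prohibit tests. A short SAP may list conventional tests in one section and say in another where the emphasis lies, and section 1.5, headed as the outcome analysis, could be read as governing outcomes. It is true that section 1.5 does not ban tests, and the sections could coexist if section 1.2 marked its P values as secondary. It does not, and no text gives section 1.5 precedence.

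Second, section 1.6 never says that significance drives outcome selection, and no conclusion about efficacy or equivalence is planned. That is correct. The risk is one of misreading and of an unspecified input, not of a stated decision rule.

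Third, the size depends on assumption. The VAP rates are assumed, 50% is a floor and not an expectation, and section 1.3 defines the analysed set as "all enrolled participants and followed up at least for 3 days in ICU". If the 50% refers to the day 6 evaluation, the set evaluable at day 3 could be well above 30, and the columns for 15 and 10 per arm would be too pessimistic. This stands as a limit on the figures. It does not touch the contradiction, and at low to moderate rates power is poor even with all 60 evaluable.

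Finally, effect measures may be set out in the protocol, which is not at hand. Their absence is therefore subordinate here: the point rests on two statements within this SAP.

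**Conclusion.** The concern holds. Section 1.2 sets an unqualified significance threshold, section 1.5 turns the analysis away from formal testing, and nothing fixes the status of the P values. That conclusion depends on no assumed figure.

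The practical size does depend on the assumptions of equal arms, doubled VAP rates, and a follow-up rate equal to the evaluable rate. For base rates of 10% to 20%, power is at most about 39% even with 30 per arm. It exceeds 80% in only one of the cases examined, 40% v 80% with all 60 evaluable in two arms. A non-significant label would be largely uninformative across the plausible low to moderate range. This should be fixed before analysis. It affects reporting and interpretation, not the conduct of the trial.

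**What to change.** Reconcile sections 1.2 and 1.5 in one of two ways:

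1. Remove the P ≤ 0.05 rule for between-group outcomes; or
2. Keep P values, label them exploratory, and state that no conclusion of difference or of no difference will be drawn from them and that they will not decide outcome selection under section 1.6.

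In either case, name in section 1.2 the estimates that carry the intervals promised in section 1.5: the risk difference for VAP and other categorical outcomes, and the mean or median difference for continuous outcomes, each with a 95% confidence interval.

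Optional additions are 95% intervals (for example Wilson) for the feasibility proportions, and a statement of expected precision over 30 to 60 evaluable participants, with 30 as the minimum and the evaluation day for the follow-up rate made explicit.

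The cost is SAP wording only, with no change to sample size or data collection. The trial gives up claims of significance, which section 1.5 already sets aside as its focus.
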